
For patients who achieve disease control following 12 months of treatment, patient questionnaires and information related to health resource use should be completed every 12 weeks relative to the date of randomisation until confirmed PD by RECIST 1.1 by investigational site review.
 
For patients who discontinue study drug due to toxicity or a reason other than confirmed PD, patient questionnaires and information related to health resource use should be completed relative to the date of randomisation as follows: every 8 weeks for the first 48 weeks (per Table 1), then every 12 weeks thereafter until confirmed PD by RECIST 1.1 by investigational site review.
								
Physical examination	X							
Vital signs (BP, pulse, respiratory rate, temperature, oxygen saturation; see Section 6.4.8 )	X							
Weight	X							
AE/SAE assessment	X	X	X					
Concomitant medications	X							
World Health Organization performance status a	X	X a	X	X a	X a	X a	X a	X a
Subsequent anticancer therapy	X	X	X	X	X	X	X	X
Survival status: phone contact with patients who refuse to return for evaluations and agree to be contacted		X	X	X	X	X	X	X (every 2 months)
Haematology	X	X	X	X				X
Serum chemistry	X	X	X					

**Table 2** Schedule of study procedures: follow-up for patients who have completed the treatment period for study drug and achieved disease control (until confirmed progression of disease) and patients who have discontinued study drug due to toxicity or a reason other than confirmed progression of disease

Evaluation	Time Since Last Dose of Study Drug							
	Day (±3)	2	3	4	6	8	10	12 Months and Every 6 Months Thereafter (±2 weeks) d
Amylase, lipase (where available)	X	X	X					
Thyroid function tests (TSH, and T3 and T4)	X							
Coagulation parameters b					As clinically indicated			
Urinalysis					As clinically indicated			
Pharmacokinetic assessment			X					
Immunogenicity assessment (ADA sampling [including ADA neutralising antibodies] to identify ADA responses in patient circulation)			X		X			
sPD-L1 concentration (to assess target engagement)							X	
Circulating soluble factors (to assess cytokines, chemokines, growth factors and antibodies against tumour and self antigens in circulation)	X					X		
miRNA/mRNA (to examine immune cell gene expression profiles in circulation)	X							

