d Patients on survival follow-up at the time of final DCO for the study will be considered to have completed the study and will continue to receive treatment per local standard of care.

ADA Anti-drug antibody; AE Adverse event; APTT Activated partial thromboplastin time; BP Blood pressure; CT Computed tomography; INR International normalised ratio; miRNA Micro RNA; MRI Magnetic resonance imaging; mRNA Messenger RNA; PD Progression of disease; RECIST Response Evaluation Criteria In Solid Tumours; SAE Serious adverse event; sPD-L1 Soluble programmed death ligand 1; T3 Triiodothyronine; T4 Thyroxine; TSH Thyroid stimulating hormone.

**Table 3** Schedule of study procedures: follow-up for patients who have discontinued study drug due to confirmed progression of disease

Evaluation	Time Since Last Dose of Study Drug						
	Day (±3)	Months (±1 week)					
		2	3	4	6	8	10
30	12 Months and Every 6 Months Thereafter (±2 weeks)						

For patients who continue on study drug post confirmed progression at the Investigator's discretion (following consultation with the sponsor), patient questionnaires and information related to health resource use should be completed relative to the date of randomisation per Table 1 until study drug is stopped.
 
For patients who discontinue study drug following confirmed progression, patient questionnaires and information related to health resource use should be completed at the Day 30 assessment only.
							
Physical examination	X						
Vital signs (BP, pulse, respiratory rate, temperature, oxygen saturation; see Section 6.4.8)	X						
Weight	X						
AE/SAE assessment	X	X	X	X	X	X	X
Concomitant medications	X	X	X	X	X	X	X
World Health Organization performance status a	X	X a	X a	X a	X a	X a	X a
Subsequent anticancer therapy	X	X	X	X	X	X	X
Survival status: phone contact with patients who refuse to return for evaluations and agree to be contacted		X	X	X	X	X	X (every 2 months)
Haematology	X	X	X	X	X	X	X
Serum chemistry	X	X	X	X	X	X	X
Amylase, lipase (where available)	X	X	X	X	X	X	X
Thyroid function tests (TSH, and T3 and T4)	X						
Coagulation parameters b							

As clinically indicated

**Table 3** Schedule of study procedures: follow-up for patients who have discontinued study drug due to confirmed progression of disease

Evaluation	Time Since Last Dose of Study Drug					

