Disease progression requires confirmation, the confirmatory scan should occur preferably at the next scheduled visit and no earlier than 4 weeks after the initial assessment of PD in the absence of clinically significant deterioration. Study treatment will continue between the initial assessment of progression and confirmation for progression. For all patients who are treated through progression and patients who achieve disease control (i.e., CR, PR or SD) through to the end of the 12 month treatment period and restart study treatment upon evidence of PD (according to RECIST 1.1), with or without confirmation, during follow-up, the investigator should ensure patients do not have any significant, unacceptable or irreversible toxicities that indicate continuing treatment will not further benefit the patient, and that the patient still meets all of the inclusion criteria and none of the exclusion criteria for this study including re-consenting to continue or restart treatment. To restart study treatment the patient must not have received an intervening systemic anti-cancer therapy post study drug discontinuation. Study drug should be discontinued if there is confirmed PD following a previous response (PR or CR) to study drug.

Patients with rapid tumour progression or with symptomatic progression that requires urgent medical intervention (eg, central nervous system metastasis, respiratory failure due to tumour compression, spinal cord compression) will not be eligible to continue to receive study drug.

Progression would be considered confirmed if the following criteria are met:

- $\geq 20\%$ increase in the sum diameters of target lesions (TLs) compared with the nadir at 2 consecutive visits with an absolute increase of at least 5 mm

The assessment of progression of $\geq 20\%$ increase in the sum diameters of TLs compared with the nadir is at the first progression time point relative to the nadir (the smallest sum of diameters and this may be at baseline or subsequent follow-up visit). The confirmed scan confirms the persistence of the $\geq 20\%$ increase relative to the nadir.

- and/or significant progression (worsening) of non target lesions (NTLs) or new lesions at the confirmatory PD time point compared with the first time point where progression of NTLs or new lesions identified
- and/or additional new unequivocal lesions at the confirmatory PD time point compared with the first time point new lesions identified.

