3.6.2 Health Resource Use

Health resource use outcome variables include the following:

- Length of hospital stay
- Reasons for hospitalisation
- Length of any time spent in an intensive care unit (ICU)

The length of hospital stay will be calculated as the difference between the date of hospital discharge (or death date) and the start date of hospitalisation or start of study drug if the start

of study drug is after start date of hospitalisation (length of hospital stay = end date of hospitalisation – start date of hospitalisation or start date of study drug whichever is later + 1). For patients with missing discharge date, the last day with available data will be used as the end date of hospitalisation.

For patients who were hospitalised more than one time during the study period, the length of hospital stay will be the sum of all durations of hospital stays.

The length of ICU stay will be calculated using the same method as detailed above for the length of hospital stay.

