4.2.9.2 Health resource use

An exploratory health economic analysis of hospital episodes including the number of hospitalisations, type of contact (hospitalisation, outpatient, day case), reason, total length of hospital stay and total length of ICU stay will be undertaken to examine the impact of disease and treatment on resource use to primarily support the economic evaluation of MEDI4736. This will include providing descriptive statistics as appropriate, including means, median,

ranges or frequencies and percentages and will be summarised by randomised treatment arm. These simple summaries will be included in the CSR. However, the exploratory health economic analysis to be performed will be described in the payer analysis plan.

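### Hospital admissions and days are summarised by arm as unadjusted totals, although resource-use collection runs essentially to confirmed progression, so the arm with longer PFS is expected to show more use at equal rates

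*SAP*

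**What the plan says.** **Collection.** Protocol Table 2 covers patients who complete 12 months with disease control and patients who stop drug for reasons other than confirmed PD. For the former, "patient questionnaires and information related to health resource use should be completed every 12 weeks relative to the date of" randomisation. For the latter, the interval is 8 weeks up to week 48 and 12 weeks after that. In both cases collection runs "until confirmed PD by RECIST 1.1 by investigational site review". Protocol Table 3 covers patients with confirmed PD. If they stop drug, "patient questionnaires and information related to health resource use should be completed at the Day 30 assessment only". If they stay on drug, the Table 1 schedule continues until drug is stopped. Only after the primary PFS and OS analyses does Protocol Table 11 collect hospital use from patients in survival follow-up as well.

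**Confirmation of PD.** The confirmatory scan is preferably at the next scheduled visit and "no earlier than 4 weeks after the initial assessment of PD" (SAP 3.1).

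**Variable.** In SAP 3.6.2, a patient's hospital stay is the discharge or death date minus the later of admission and first dose, plus one day. With several admissions, "the length of hospital stay will be the sum of all durations of hospital stays". ICU stay is handled the same way.

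**Summary.** SAP 4.2.9.2 plans an exploratory summary of hospital contacts, "including the number of hospitalisations, type of contact (hospitalisation, outpatient, day case), reason, total length of hospital stay and total length of ICU stay". It uses means, medians, ranges, frequencies and percentages by randomised arm, reported in the CSR. The same section adds that "the exploratory health economic analysis to be performed will be described in the payer analysis plan".

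**Elsewhere.** SAP 4.2.4.1 gives AE event rates per 100 patient-years.

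**The concern.** The time over which a patient can contribute an admission ends shortly after confirmed progression for most patients. Progression is what MEDI4736 is designed to delay, so the length of observation depends on treatment. A sum of days or a count of admissions mixes the rate of hospital use with the length of observation.

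The stated exploratory objective is to describe and evaluate resource use associated with MEDI4736 and the underlying disease. If the two arms had the same admission rate, the CSR table would still show higher mean totals on MEDI4736, and a modest true reduction in rate could be hidden. The primary and key secondary analyses are unaffected.

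**Working it through.** **Reproducing the plan's own figure.** The documents give no number for hospital use, so the check starts from the PFS design that drives the window. With 458 events, HR 0.67, 2:1 allocation and 2.5% two-sided, power = Φ(|ln 0.67| × √(458 × 1/3 × 2/3) − 2.241) = 96.4%. The critical HR is exp(−2.241/√(458 × 2/9)) = 0.80. Both agree with the stated figures of at least 95% and 0.8.

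**Inputs (SAP 1.3).** Exponential PFS with medians of 15 and 10 months; accrual 22 months plus follow-up 14 months, so the PFS cut-off is at month 36. Assumed here: uniform accrual, so potential follow-up C is uniform from 14 to 36 months; a constant admission rate; all randomised patients in the denominator; a lag L from PD to the end of collection. L = 1 to 3 months represents the Day 30 record with up to about 8 weeks for confirmation.

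**Formula.** Mean window = E[min(PFS + L, C)] = L + (1/λ) × {1 − [e^(−λ(14−L)) − e^(−λ(36−L))]/(22λ)}, with λ = ln 2/median (0.0693 placebo, 0.0462 MEDI4736). At equal constant rates, the ratio of mean totals equals the ratio of mean windows.

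For L = 0:
- Placebo: 14.43 × (1 − (0.379 − 0.082)/1.525) = 11.6 months.
- MEDI4736: 21.64 × (1 − (0.524 − 0.189)/1.017) = 14.5 months.

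| Lag after PD | MEDI4736 (months) | Placebo (months) | Ratio |
|---|---|---|---|
| 0 | 14.5 | 11.6 | 1.25 |
| 1 month | 15.2 | 12.4 | 1.22 |
| 3 months | 16.5 | 14.0 | 1.18 |

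On these assumptions, a true 15% lower admission rate would show as 0.85 × 1.18 = 1.00 to 0.85 × 1.22 = 1.04.

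**Calibration.** Uniform accrual without dropout gives about 503 PFS events at month 36, against 458 planned. Bringing this to 458 with about 11% dropout per year gives ratios of 1.24 with no lag and 1.17 with 8-week confirmation plus Day 30. Using later-weighted accrual instead gives 1.21 and 1.15. The documents state no dropout rate.

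**Relaxing the constant rate (assumed scenarios).**
- *Early peak.* Suppose the rate in the first 6 months is k times the later rate. Then the mean is proportional to k × E[min(W, 6)] + E[max(W − 6, 0)], where W is the window. For k = 2 and a 1-month lag: (2 × 5.46 + 9.73)/(2 × 5.23 + 7.20) = 1.17. For k = 3 and a 3-month lag: (3 × 5.80 + 10.67)/(3 × 5.71 + 8.27) = 1.11.
- *Admissions at PD.* Take 0.5 stays per year plus a 20% or 30% chance of an admission at PD. The proportion progressing by the cut-off is 0.671 on MEDI4736 and 0.806 on placebo. With 20% and a 1-month lag: (0.633 + 0.134)/(0.518 + 0.161) = 1.13. With 30% and a 3-month lag: (0.686 + 0.201)/(0.582 + 0.242) = 1.08.

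These scenarios span about 8-17%.

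**Changing the denominator.** If days are summarised only among hospitalised patients, divide by the ratio of proportions ever hospitalised. With a 1-month lag and assumed rates of 0.3, 0.5 and 1.0 stays per year, this gives 1.223/1.188 = 1.03, 1.223/1.168 = 1.05 and 1.223/1.130 = 1.08.

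**The case against.** The strongest reply is that these are what SAP 4.2.9.2 calls them: simple descriptive summaries of an exploratory outcome. No test or treatment contrast is specified, and Protocol 12.2.11 says only that the analysis may be undertaken. The health economic analysis sits in a payer analysis plan that may well use person-time or health states. All of that stands. A reader might infer that the economic evaluation itself will be biased against MEDI4736; the documents do not support this, because that plan is not among them. What remains is that the by-arm totals go into the CSR whatever the payer plan does.

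A reader might also infer that collection simply stops at progression. It does not: there is the Day 30 record, continued collection while drug is given beyond PD, and Protocol Table 11 in the long-term phase. The window also follows site-confirmed PD, whereas the calculation uses the design medians for PFS by central review. These points make the window longer or less exactly tied to the PFS endpoint, but they do not make it equal between arms.

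The size is assumption-dependent. SAP 3.6.2 does not say whether patients never admitted count as zero days. Medians would move little: at 0.3 to 0.5 stays per year the all-patient median is zero in both arms. An early peak is plausible, since Protocol 5.5.3.1 places radiation pneumonitis symptoms at 1 to 3 months after radiotherapy.

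Finally, total hospital use while progression-free is a legitimate quantity, and patients who stay progression-free longer do accrue more of it. That argues for keeping the totals, but a reader still needs the observation time to interpret them.

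**Conclusion.** The point holds as a cheap improvement to an exploratory, descriptive output. The collection window depends on an outcome that treatment is expected to change, and the planned by-arm totals make no allowance for it.

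Mean totals on MEDI4736 would be inflated by about 18-22% at equal rates for a 1- to 3-month lag after PD, and by 25% with no lag. This rests on the design PFS medians, uniform 22-month accrual, a 36-month cut-off, a constant admission rate and an all-patient denominator. The figure is about 8-17% under the assumed early-peak or progression-clustered scenarios, and about 3-8% for days among hospitalised patients only. A flat statement that MEDI4736 will appear to use a fifth more hospital care is therefore stronger than the documents allow: the direction is expected, but the size is conditional.

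**What to change.** In SAP 4.2.9.2, add hospitalisations, hospital days and ICU days per patient-year of resource-use collection, by randomised arm, counting patients never admitted as zero. Start the clock at randomisation and end it at the earliest of the last resource-use assessment, death or DCO. Align the start date in SAP 3.6.2, which now uses first dose where that is later than admission; otherwise patients randomised but never treated have no defined denominator. Show collection time by arm and keep the raw totals beside the rates.

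The cost is minor programming from dates already collected, with no protocol change and no new data. The limitation is that the rate still describes mainly time before progression, which a footnote to the table should say.

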4. ANALYSIS METHODS

There will be 1 treatment comparison of interest:

- MEDI4736 10 mg/kg vs placebo

The co-primary endpoints are OS and PFS using RECIST 1.1. The study has been sized to characterise the OS and PFS benefit of MEDI4736 relative to placebo.

Results of all statistical analysis will be presented using a 95% CI and 2-sided p-value, unless otherwise stated.

4.1 General Principles

Efficacy and HRQoL data will be summarised and analysed on the ITT analysis set. Safety and treatment exposure data will be summarised based upon the safety analysis set. Study population and demography data will be summarised based upon the ITT analysis set.

Efficacy from the re-treatment period may be summarised separately for the site investigator data. For the site investigator data, any derivations relative to baseline (e.g. day, RECIST derivations) in the re-treatment period will be relative to the baseline scan prior to the re-treatment. To avoid biasing the blinded central reviewers (i.e., when determining progression) the baseline scans prior to re-treatment will not be identified (see further the BICR charter) thus no efficacy data will be summarised from the re-treatment period based upon BICR.

Safety data will be summarised from the initial treatment period. Safety data from the re-treatment period may also be summarised via a small set of headline summaries should there be sufficient number of patients re-treated to warrant this. Any safety summaries representing the re-treatment period will be based upon a subset of the safety analysis set representing patients who have had at least one dose of study treatment in the re-treatment period.

The below mentioned general principles will be followed throughout the study:

- Descriptive statistics will be used for all variables, as appropriate. Continuous variables will be summarised by the number of observations, mean, standard deviation, median,

minimum, and maximum. For log transformed data it is more appropriate to present geometric mean, coefficient of variation (CV), median, minimum and maximum. Categorical variables will be summarised by frequency counts and percentages for each category.

- Unless otherwise stated, percentages will be calculated out of the population total and for each treatment group.
- For continuous data the mean and median will be rounded to 1 additional decimal place compared to the original data. The standard deviation will be rounded to 2 additional decimal places compared to the original data. Minimum and maximum will be displayed with the same accuracy as the original data.
- For categorical data, percentages will be rounded to 1 decimal place.
- SAS® version 9.2 will be used for all analyses.

4.1.1 Baseline

In general, for efficacy and PRO endpoints the last observed measurement prior to randomization will be considered the baseline measurement. However, if an evaluable assessment is only available after randomization but before the first dose of randomized treatment then this assessment will be used as baseline. For safety endpoints the last observation before the first dose of study treatment will be considered the baseline measurement unless otherwise specified. For assessments on the day of first dose where time is not captured, a nominal pre-dose indicator, if available, will serve as sufficient evidence that the assessment occurred prior to first dose.

Assessments on the day of the first dose where neither time nor a nominal pre-dose indicator are captured will be considered prior to the first dose if such procedures are required by the protocol to be conducted before the first dose.

In all summaries change from baseline variables will be calculated as the post-treatment value minus the value at baseline. The % change from baseline will be calculated as (post-baseline value - baseline value) / baseline value x 100.

4.1.2 Multiplicity

The multiple testing procedure will define which significance levels should be applied to the interpretation of the raw p-values for the 2 primary endpoints of PFS and OS and the key secondary endpoints of OS24 and ORR.

There will be 4 DCO time points in the study. The DCO for the interim PFS analysis (first analysis) will be done when 367 PFS events have occurred (52% maturity), approximately 30 months after the first patient is randomised. The DCO for the primary PFS analysis (second analysis) and interim OS analysis will be done when at least 458 PFS events have occurred

(65% maturity) at approximately 36 months after first patient is randomised. It is expected that approximately 285 death events (41% maturity) will be available for the interim OS analysis. The third analysis data cut-off will occur at the time of the second OS interim analysis when it is expected that 393 OS events have occurred (56% maturity, approximately 47 months after the first patient is randomised). The DCO for the primary OS analysis (fourth analysis) will be done when 491 OS events have occurred (70% maturity) at approximately 62 months.

The overall 5% type 1 error will be split between the co-primary endpoints OS and PFS. An alpha level of 2.5% will be allocated to OS analysis and an alpha level of 2.5% will be allocated to the PFS analysis. An interim PFS analysis for superiority will occur when approximately 367 PFS events have occurred and the primary PFS analysis will be performed when 458 PFS events have accumulated. The 2.5% alpha level allocated to PFS will be controlled at the interim and primary time point by using the Lan DeMets ([Lan and DeMets 1983](#)) spending function that approximates an O'Brien Fleming approach, where the significance level applied at the interim depends upon the proportion of information available. If 80% of the PFS events required at the time of the primary PFS analysis is available at the time of the interim (i.e., 367/458 PFS events have occurred), the 2-sided significance level to be applied for the PFS interim analysis would be 1.04% and the 2-sided significance level to be applied for the primary PFS analysis would be 2.19%.

An interim OS analysis for superiority will occur at the time of the primary PFS analysis. The 2.5% alpha level allocated to OS will be controlled at the 2 interim and primary time point by using the Lan DeMets ([Lan and DeMets 1983](#)) spending function that approximates an O'Brien Fleming approach, where the significance level applied at the interim depends upon the proportion of information available. For example, if 58% or 80% of OS events required at the time of the primary OS analysis is available at the time of the interim (i.e., 285/491 or 393/491 events have occurred), the 2-sided significance level to be applied for the OS interim analysis would be 0.21% and 0.98% and the 2-sided significance level to be applied for the primary OS analysis would be 2.17%.

The family wise error rate (FWER) will be strongly controlled for the testing of PFS, OS, OS24, and ORR including interim analyses by applying the testing procedure illustrated in the Figure 2 below.

The PFS and OS will be tested according to the group sequential Holm fixed (GSHf) procedure described in [Ye et al 2012](#). In this procedure, the testing will start from PFS, if the testing for PFS is significant at the alpha level specified in Figure 2 at either interim or primary analysis the full 2.5% alpha level for PFS can be propagated to the testing of OS, which means that the OS will be tested at an overall alpha level of 5%. Following the GSHf procedure the alpha level for the interim analyses of OS will not be changed but the alpha level for the primary analysis of OS will be recalculated based on 5% alpha level overall with interim alpha levels as specified in Figure 2. For example, if the information fraction for the interim analyses is as specified (80% for PFS interim and 58%/80% for OS interims) the alpha level for the primary OS analysis will be 4.85% so that the FWER for OS is 5% accounting

[figure not shown]
for interim analyses, given testing of PFS is significant at interim ($\alpha=1.04\%$) or at primary analysis ($\alpha=2.19\%$). The alpha level for the interim OS analyses will remain at 0.21% and 0.98%.

If the testing for PFS is not significant at either the interim ($\alpha=1.04\%$) or at the primary analysis ($\alpha=2.19\%$), the OS will be tested at the levels specified in [Figure 2](#). In this case if the testing for OS is significant at any interim analysis or primary analysis the full 2.5% alpha level for OS can be propagated to the testing of PFS, which means that the PFS will be tested at an overall alpha level of 5%. Following GSHf, the alpha level for the interim analysis of PFS will not be changed but the alpha level for the primary analysis of PFS will be recalculated based on 5% alpha level overall with interim alpha levels as specified in [Figure 2](#). For example, if the information fraction for the interim analyses is as specified (80% for PFS interim and 58%/80% for OS interim) the alpha level for the primary PFS analysis will be 4.88%, given testing of OS is significant at interim ($\alpha=0.21\%$ and 0.98%) or at primary analysis ($\alpha=2.17\%$). The alpha level for the interim PFS analysis will remain at 1.04%.

OS24 and ORR will not be tested unless the null hypotheses for both PFS and OS are rejected according to the GSHf procedure described above. After both PFS and OS are rejected the OS24 will be tested with 5% alpha level controlled at the interim and primary time point. The interim analyses of OS24 will use the same interim alpha level for OS at the same analysis point. The alpha for primary analysis of OS24 will be calculated based on interim alpha levels and information fractions at the interim so that the alpha level for OS24 is controlled at 5% overall. ORR will only be tested after the null hypothesis of PFS, OS, and OS24 are all rejected and ORR will be tested at a 5% level.

The FWER is strongly controlled at 5% for PFS and OS according to [Ye et al 2012](#). The FWER for PFS, OS, and OS24 is also strongly controlled at 5% due to the fix-sequence testing nature and according to [Glimm et al 2009](#). Finally the FWER is still strongly controlled after adding the fix-sequence testing of ORR. So the FWER is strongly controlled at 5% for the testing of all four endpoints. [Figure 2](#) shows the multiple testing framework.

Figure 2 Multiple testing procedures for controlling the type 1 error rate

